4.1.2. Study Procedures and Assessments

For each participant, the study will include:

1. **Screening:** Participants with a locally determined *BRAF* V600E mutation will provide informed consent for screening and study procedures and assessments and will be screened for eligibility in the 28 days before the first dose of encorafenib.
2. **Treatment Period:** Participants fulfilling all the eligibility criteria (see Section 5) will receive encorafenib 300 mg QD in 28 day (\pm 7 days) cycles until death, disease progression⁴ or one of the other predefined criteria for study treatment discontinuation is met (see Section 7.1). An end of treatment visit will be completed at the time of study treatment discontinuation (as soon as possible and \leq 14 days after the last dose of study treatment).
3. **A 30-day Safety Follow-up:** A safety follow-up visit will be performed approximately 30 days after the last dose of study treatment or before the initiation of subsequent anticancer therapy, whichever occurs first.

The schedule of activities for each participant is shown in Table 1.

Tumor assessments will be performed by radiological imaging (including computed tomography [CT], magnetic resonance imaging [MRI], X-ray, different methods of whole-body bone scans). Tumor overall assessment (response, stable disease, progressive disease) will be determined locally by the investigator according to RECIST Version 1.1 (see Appendix 10.7). Tumor assessments will be performed at screening/baseline (within 28 days prior to the first dose of study treatment), then at least every 8 weeks (\pm 7 days) for the first 12 months, then at least every 12 weeks (\pm 7 days) until disease progression, withdrawal of consent for treatment, initiation of subsequent anticancer therapy, participant is lost to follow-up, or death (whichever occurs first). More frequently tumor assessments may be performed if needed.

Safety assessments include monitoring of adverse events, DLTs, physical examinations, dermatological examinations, clinical laboratory safety tests (hematology, clinical chemistry, coagulation, urinalysis), vital signs, electrocardiograms (ECGs), and Eastern Co-operative Oncology Group (ECOG) performance status.

Serial blood samples to characterize the PK profile of encorafenib and its metabolites (LHY746) will be collected from participants on the first day of treatment (Cycle 1 Day 1) and at steady state after 1 month treatment (Cycle 2 Day 1).

4.2. Scientific Rationale for Study Design

The study design involves a 3+3 approach (commonly used in conducting phase 1 oncology studies) that allows the assessment of DLTs but does not include a dose escalation or de-escalation

⁴ In special circumstances, continuation of treatment beyond disease progression may be allowed (see Section 6.1).

component. It is a well-established design for selecting a dose suitable for further investigation whilst minimising unnecessary exposure. In this study the design is employed to confirm the safety and tolerability of encorafenib 300 mg QD monotherapy in Chinese participants with *BRAF* V600E mutant melanoma or NSCLC to support further clinical development in combination with binimatinib.

4.3. Justification for Dose

The dose of encorafenib is 300 mg per oral (PO) QD, corresponding to its single agent RP2D. This dose has also been shown in clinical studies to result in tumor regression and clinical responses as a single agent [Dummer 2013, Gomez-Roca 2014] (see Section 2.1.4).

Permitted dose modifications are detailed in Section 6.6.

4.4. End of Study Definition

The end of study is defined as the timepoint when the last participant enrolled has discontinued study treatment and completed the 30-day safety follow-up.

5. Study Population

It is planned to treat up to six participants with metastatic *BRAF* V600E mutant melanoma or NSCLC who are *BRAF* inhibitor treatment-naïve and have failed the previous therapy(ies) for metastatic disease or are not eligible to standard therapy. The sample size rationale is provided in Section 9.2.

Prospective approval of protocol deviations to recruitment and enrolment criteria, also known as protocol waivers or exemptions, is not permitted.

Each participant fulfilling all inclusion criteria and none of the exclusion criteria will be eligible.

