Study Principal Investigator:	PII [REDACTED]
Number of participants	Up to 6 evaluable participants will be enrolled in the study which will be conducted at two or three sites in mainland China.
Treatment group and duration	
Encorafenib will be administered as a fixed, flat oral dose of 300 mg QD.
 
Study treatment will be administered in 28-day cycles until death, disease progression or one of the other predefined criteria for study treatment discontinuation is met.
 
 • If the study treatment is discontinued, the participant will have an end of treatment visit followed by a 30-day safety follow-up assessment 
Recruitment duration: 6 months.
 
Estimated duration of the follow-up period after last participant in: approximately 6 months.

Trial Steering Committee:	The trial steering committee (TSC) will analyse the available safety data and assess the toxicities as significant or not once the first three participants (and six participants if required) have fully completed the first cycle of treatment (28 days). The TSC will determine if encorafenib 300 mg QD is tolerable based on the DLT rate (DLTs observed

	
in <33% of participants) and evaluation of the overall toxicity profile (based on deaths, treatment emergent SAEs, treatment emergent adverse events (TEAEs) leading to discontinuation and to dose interruption/reduction).
 
The TSC will make a recommendation if the dose of encorafenib 300 mg QD is not deemed tolerable.

--	--

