Encorafenib will be orally self-administered. A fixed-flat dose of 300 mg PO encorafenib will be administered QD. Encorafenib should be taken daily in the morning at approximately the same time (\pm 2 hours) every day without regard to food. If a participant vomits at any time after dosing, the dose should not be re-administered. Doses of encorafenib that are omitted for adverse events or any other reason should not be made up during the day, or at the end of the dosing period.

The first dose of encorafenib will be taken on Cycle 1 Day 1 and will then be continuously self-administered in 28-day cycles until death, disease progression, one of the other criteria for study treatment discontinuation is met (see Section 7.1) or the participant is lost to follow-up (see Section 7.3). On Day 1 of each cycle the encorafenib dose will be administered at the study site.

Lifestyle considerations in relation to dosing are detailed in Section 5.3. There are no restrictions on dosing in relation to the timing of meals.

Participants will receive a diary to document self-administration of encorafenib to include the dose, date of dosing (and time if applicable), if the participant vomited after dosing, if any doses were missed and the reason for the missed dose. One diary will be provided per cycle. On the days when encorafenib is administered at the study site, these details will be recorded in the eCRF by the study site personnel.

Management of dose modifications (including dose interruptions and retreatment) are detailed in Section 6.6.

Continuing study treatment beyond disease progression for any participant is only to be considered under special circumstances when it is believed that the participant may clinically benefit from continued treatment beyond progression. If it is judged by the investigator (in consultation with the sponsor) to be in the best interest of the participant, the participant may remain on study treatment as long he/she continues to benefit from the study treatment according to the investigator's assessment. Special circumstances can be defined by e.g. mixed responses and appearance of new brain metastases (only) which is treatable with stereotactic radiotherapy or surgery but does not require whole brain radiotherapy.

Treatment beyond progression is not allowed in the following cases:

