6.3.2. Participant Numbering

A participant will be considered enrolled into the study as soon as he/she has signed the ICF. All participants who provide informed consent will be assigned a unique participant code by an Interactive Response Technology (IRT) system. Once a participant is enrolled, he/she will be identified only by the assigned participant code. Once assigned, a participant code must not be reused for any other participant.

The participant code will contain eight digits, corresponding to the country number, the site number and the participant's number according to chronological order (once having provided written informed consent).

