7.1.2. Permanent Study Treatment Discontinuation

Study treatment is to be administered until any of the following criteria for permanent discontinuation is met:

- Disease progression, as defined by Response Evaluation Criteria in Solid Tumors (RECIST) Version 1.1 (continuation of treatment beyond progression is permitted in special circumstances, see **Section 6.1**).

- Clinical progression, as determined by the investigator in the absence of radiographic progression.
- Withdrawal of consent. Participants may choose to withdraw consent to continue study treatment but remain in the study to be followed for safety and disease progression. In this case, follow-up data will continue to be collected for this participant. Withdrawal of consent for study treatment may occur at any time without penalty of jeopardizing their healthcare or loss of benefits to which they are otherwise entitled. Participants who withdraw consent to study treatment and follow-up, will no longer receive study treatment or followed up within this study.
- Unacceptable adverse events or failure to tolerate study treatment:
 - Grade 4 or life-threatening adverse event as outlined in Appendix 10.4 (except with approval from the sponsor's medical monitor)
 - Toxicity requiring more than the allowed number of dose reductions for encorafenib, (see **Table 7**).
 - Occurrence of an adverse event that is related to study treatment and compromises the participant's ability to continue study-specific procedures according to investigator's judgement or is considered to not be in the participant's best interest. The medical monitor or delegate should immediately be informed by phone or e-mail and a report explaining the discontinuation will be forwarded to him/her as soon as possible.
- Initiation of subsequent anticancer therapy.
- Participant is non-compliant with study procedures or study treatment that in the judgment of the investigator or sponsor renders the participant unsuitable.
- Significant protocol deviation that, in the opinion of the investigator and/or sponsor, renders the participant unsuitable for further study treatment administration.
- Participant has missed >4 weeks (i.e., 28 consecutive days) of dosing (see Section 7.1.1).
- Participant becomes pregnant or begins breastfeeding.
- Participant is lost to follow-up.
- Defined end of the study (see Section 4.4)

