1.2.4. End Of Study Definition

The end of study is defined as the timepoint when the last participant enrolled has discontinued study treatment and completed the 30-day safety follow-up.

2. Statistical Hypotheses

Because of the exploratory nature of the study, all data will be analyzed descriptively and not with an inferential approach. No formal statistical testing will therefore be performed.

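### The end of study is keyed to the last participant enrolled and is also a criterion for stopping treatment: read literally it takes earlier participants off drug, and read loosely the criterion can never apply

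*Protocol*

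**What the plan says.** Protocol Section 4.4 defines the end of study through one person: "The end of study is defined as the timepoint when the last participant enrolled has discontinued study treatment and completed the 30-day safety follow-up". SAP 1.2.4 uses the same trigger ("the last participant enrolled has discontinued study treatment and completed the 30-day safety follow-up"), and SAP 1.2 repeats it when it places the final analysis at the end of study.

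Protocol Section 7.1.2 opens its list of stopping criteria with "Study treatment is to be administered until any of the following criteria for permanent discontinuation is met". One entry is "Defined end of the study (see Section 4.4". Termination by the sponsor or the competent authority is a separate entry.

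Treatment has no fixed maximum. Section 6.1 has encorafenib "continuously self-administered in 28-day cycles until death, disease progression, one of the other criteria for study treatment discontinuation is met", with a cross-reference to Section 7.1. In special circumstances after progression, "the participant may remain on study treatment as long he/she continues to benefit from the study treatment". The sample is small: "Up to 6 evaluable participants will be enrolled in the study".

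The documents contain no rollover, extension or continued-access provision, and no exception for a participant who is on treatment when the end of study is reached.

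**The concern.** The last participant enrolled need not be the last to stop treatment. If that person stops early, the Section 4.4 condition is met about 30 days later, and the Section 7.1.2 criterion then applies to everyone still on drug.

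Three things depend on how the definition is read:

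- whether a participant who is still benefiting stays on treatment;
- how much on-treatment exposure, and hence late-emerging safety data, the study collects;
- when the final analysis is run.

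In a safety study of three to six people, losing the later exposure of one or two participants is a material share of the information.

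**Working it through.** The plan gives no figure on this point, so the check is first one of wording and then an illustration of size.

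**The two readings**

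| | Literal: the person enrolled last | Loose: the last of all participants to finish |
|---|---|---|
| Trigger (4.4) | That person's 30-day follow-up is complete | Every participant's 30-day follow-up is complete |
| Anyone still on drug? | Possibly | No |
| End-of-study entry in 7.1.2 | Discontinues those still on drug | Can never operate |
| SAP 1.2 committee meeting, held during the study once every subject has completed the safety follow-up | Can fall after the end of study | Fits |
| End-of-treatment visit and 30-day follow-up required by 7.1.2 after discontinuation | Fall after the end of study for those discontinued by it | Fit |

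Neither column leaves all the text working.

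**How often it would matter under the literal reading (illustration only)**

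Inputs from the documents: 3 or 6 participants; 6 months of recruitment (Protocol 1.1); 30-day follow-up, taken as 1 month. Median PFS figures: 5.5 months (Protocol 2.1.3, dabrafenib in NSCLC), 9.6 months (2.1.4, encorafenib 300 mg QD in the phase 3 melanoma study) and 12.4 months (2.1.4, BRAF inhibitor-naïve participants in the phase 1 dose expansion, where melanoma participants are described as treated at the MTD, declared as 450 mg QD).

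Assumptions: PFS stands in for time on drug; durations are independent and exponential; entry is evenly spaced, at months 0, 3, 6 for n=3 and every 1.2 months from 0 to 6 for n=6.

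Let m be the median, and let participant i enter g_i months before the last one. Participant i is still on drug at the literal end of study if their duration exceeds g_i + 1 plus the last participant's duration. Put a_i = 2^(-(g_i + 1)/m). For an exponential duration D, U = 2^(-D/m) is uniform on (0, 1), so

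P(at least one earlier participant on drug) = 1 - ∫₀¹ ∏(1 - a_i u) du.

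For n=3, with g = 6 and 3, this is (a₁ + a₂)/2 - a₁a₂/3:

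- m = 5.5: a₁ = 2^(-7/5.5) = 0.414, a₂ = 2^(-4/5.5) = 0.604; P = 0.509 - 0.083 = 0.426.
- m = 9.6: a₁ = 0.603, a₂ = 0.749; P = 0.676 - 0.151 = 0.526 (to rounding).
- m = 12.4: a₁ = 0.676, a₂ = 0.800; P = 0.738 - 0.180 = 0.558.

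For n=6, with g = 6, 4.8, 3.6, 2.4 and 1.2, the same integral gives 0.714, 0.770 and 0.786.

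| Assumed median (months) | n = 3 | n = 6 |
|---|---|---|
| 5.5 | 43% | 71% |
| 9.6 | 53% | 77% |
| 12.4 | 56% | 79% |

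The accrual assumption matters somewhat. With uniform random entry over 6 months, a simulation of 400,000 runs gave 0.52-0.60 for n=3 and 0.74-0.80 for n=6. If all start together and the lag is ignored, exchangeability alone gives (n - 1)/n, that is 2/3 and 5/6.

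**The case against.** The strongest reply is that nobody would apply Section 4.4 literally. SAP 1.2 plans a steering committee meeting, among the activities during the study, after every subject has completed the 30-day safety visit. That cannot precede an end of study triggered while some subjects are still on drug, so the sponsor probably meant the last of all participants to finish. This stands as evidence of intent. It does not repair the text, because Section 4.4 says something else and the loose reading leaves the 7.1.2 entry without effect.

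Three stronger readings are tempting, and the documents do not support them.

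- **That Sections 4.1.2 and 6.1 are contradicted.** Both defer to the criteria in Section 7.1, so they already take in the end-of-study entry. The problem lies between 4.4 and 7.1.2.
- **That a screen failure could end the study.** Section 6.3.2 says "A participant will be considered enrolled into the study as soon as he/she has signed the ICF", so a reader might infer that someone never treated could be the last enrolled. Such a person cannot discontinue treatment or complete follow-up after it, so cannot trigger the end of study. The design text also uses enrolment for people who receive encorafenib.
- **That safety follow-up is cut off outright.** Adverse events are collected to each participant's own 30-day visit (8.4.1), the TEAE window runs from each participant's own last dose (9.4.3.1.2), and anyone withdrawn from treatment has an end-of-treatment visit and 30-day follow-up (7.1.2). Monitoring for secondary malignancies is recommended, where clinically appropriate, for up to 6 months after the last dose. What the literal reading shortens is time on treatment and the events that longer treatment would have shown.

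It is also fair to say that the probabilities apply only under the literal reading and rest on borrowed PFS figures, only one of them clearly from encorafenib 300 mg QD.

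**Conclusion.** The concern holds as a conflict of wording with real consequences. As written, Sections 4.4 and 7.1.2 let one participant's course end treatment for others; the reading that avoids this makes a listed stopping criterion inoperative. SAP 1.2 favours that second reading but does not settle the matter.

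Under the literal reading the situation would be common: about 43-56% with 3 participants and 71-79% with 6. These figures show order of magnitude only. They assume exponential time on drug, evenly spaced entry, a 1-month lag and PFS as a proxy. The primary endpoint, DLTs in Cycle 1, is hardly touched; the stake is treatment continuity, longer-term safety exposure and the timing of the final analysis. The point should be corrected, but it does not undermine the design.

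**What to change.** Reconcile Protocol Sections 4.4 and 7.1.2 with SAP 1.2 and 1.2.4 so that:

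- the end-of-study event and the timing of the final analysis do not depend on enrolment order, and agree with the SAP 1.2 meeting that waits for every subject's safety follow-up;
- the protocol states what happens to any participant still on treatment when that point is reached, and Section 7.1.2 is consistent with it.

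Which clinical rule applies to those participants is for the sponsor to decide; the passages only need to say one thing.

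The cost is a few words in the protocol and the SAP. The study may stay open longer if one participant remains on drug, possibly beyond the roughly 6 months of follow-up after last participant in that the synopsis estimates.

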5.1. Inclusion Criteria

All the following inclusion criteria must be met for a participant to be eligible for this study:

1. Provide a signed and dated informed consent form (ICF).
2. Chinese male or female with age ≥ 18 years old at the time of the informed consent.
3. Documented histology- and/or cytology-confirmed metastatic melanoma or NSCLC (i.e. adenocarcinoma, large cell carcinoma, squamous cell carcinoma).
4. Presence of *BRAF* V600E mutation as determined by a local laboratory with a NMPA approved *BRAF* test.
5. *BRAF* inhibitor treatment-naïve participants and having failed the previous therapy(ies) for metastatic disease or are not eligible to standard therapy.

Note:

Alternative chemotherapy regimen is permitted if participants were platinum intolerant or ineligible.

6. At least one tumor lesion as per investigator assessment according to RECIST Version 1.1, which has neither been irradiated nor biopsied during the screening period. The irradiated lesion is acceptable only if it is proven as disease progression deemed measurable prior to study.
7. Life expectancy ≥ 3 months.
8. ECOG performance status of 0 or 1.
9. Adequate hematologic function at screening and baseline characterized by the following:
 - a. *Absolute neutrophil count $\geq 1.5 \times 10^9/L$.*
 - b. *Hemoglobin ≥ 90 g/L.*
 - c. *Platelets $\geq 100 \times 10^9/L$.*

d. *International normalized ratio, prothrombin time or (activated) partial thromboplastin time $\leq 1.5 \times$ upper limit of normal (ULN).*

10. Adequate hepatic function at screening and baseline characterized by the following:

- Total bilirubin $\leq 1.5 \times$ ULN.*
Note: Total bilirubin $> 1.5 \times$ ULN is allowed if indirect bilirubin is $\leq 1.5 \times$ ULN.
- Alanine aminotransferase and aspartate aminotransferase $\leq 2.5 \times$ ULN or $\leq 5 \times$ ULN in case of documented liver metastases.*

11. Adequate renal function at screening and baseline characterized by the following:

- Serum creatinine $\leq 1.5 \times$ ULN.*
- Creatinine clearance ≥ 50 mL/min as calculated by the Cockcroft-Gault formula; or estimated glomerular filtration rate > 50 mL/min/1.72m².*

12. Able to comply with the study protocol as per investigator assessment including oral drug intake, complying scheduled visits, treatment plan, laboratory tests and other study procedures.

13. Women are either postmenopausal for at least 1 year, or are surgically sterile for at least 6 weeks, or women of childbearing potential (WOCBP) must agree to take appropriate precautions to avoid pregnancy.

Appropriate precautions to avoid pregnancy for WOCBP:

- Must have negative serum β -human chorionic gonadotropin (HCG) test at screening.
- Must agree to use highly effective methods of contraception from screening until 30 days after the last dose of the study treatment.
- Must not donate ova from screening until 30 days after the last dose of study treatment.

14. Men must agree not to father child until 90 days after the last dose of study treatment.

Note:

- Must agree to use highly effective method of contraception to avoid fathering a child from screening until 90 days after the last dose of study treatment.
- Must not donate sperm from screening until 90 days after the last dose of study treatment.

5.2. Exclusion Criteria

Participants meeting any of the following criteria are not eligible to be included in this study:

1. Known immediate or delayed hypersensitivity reaction or idiosyncrasy to drugs chemically related to encorafenib, or its excipients.

2. For metastatic NSCLC: documented anaplastic lymphoma kinase (ALK) fusion oncogene, ROS1 (c-ros oncogene 1) rearrangement or epidermal growth factor receptor (EGFR) sensitizing or driver mutation.
3. Receipt of anticancer medications or investigational drugs within intervals before the first administration of study treatment.
 - a. *Prior anticancer therapy:*
 - i. *Chemotherapy and targeted small molecules (e.g. erlotinib, crizotinib): ≤28 days or 5 half-lives, with a minimum of 14 days.*
 - ii. *Biologics (e.g. immunotherapy, bevacizumab): ≤28 days or 5 half-lives.*
 - b. *Investigational agents: ≤4 weeks or 5 half-lives, with a minimum of 14 days. For investigational agents with long half-lives, enrolment before the 5th half-life requires medical monitor approval.*
 - c. *Palliative radiation therapy must be complete 7 days prior to the first dose of study treatment.*
4. Symptomatic brain metastasis.

Note: participants with previously treated or untreated asymptomatic brain metastases confirmed by CT or MRI may participate provided:

- *Participants are stable (e.g. no evidence of progression by radiographic imaging for at least 28 days before the first dose of study treatment and neurologic symptoms must have returned to baseline) and do not need any treatment within 14 days prior to study treatment.*
- *Participants must have no evidence of new or enlarging brain metastases or edema.*
- *Lesions are <1 cm in the longest diameter.*
- *Participants must have discontinued the use of steroids at least 14 days before the first dose of study treatment.*

5. Leptomeningeal disease.

6. Participant has not recovered to ≤Grade 1 from toxic effects of prior therapy and/or complications from prior surgical treatment before starting study treatment.

Note: Stable chronic conditions (≤Grade 2) that are not expected to resolve (e.g. neuropathy, myalgia, alopecia and prior therapy-related endocrinopathies) are exceptions.

7. Current use of prohibited medication ≤1 week prior to start of the study treatment and/or concomitantly.

Note:

- i. Of which herbal medications/supplements including use of St John's Wort (*hypericum perforatum*) and traditional Chinese medicines or any medications or food susceptible to be moderate or strong inhibitors cytochrome P450 (CYP) 3A4/5.*
 - ii. However, participants who either discontinue moderate or strong inhibitors or inducers of CYP3A4/5 or switch to another medication at least 7 days prior to starting study treatment are eligible.*
8. Impairment of gastrointestinal function or disease which may significantly alter the absorption of oral study treatment.
e.g. uncontrolled nausea, vomiting or diarrhea, malabsorption syndrome, small bowel resection.
9. Impaired cardiovascular function or clinically significant cardiovascular diseases.
Including any of the following:
 - a. History of acute myocardial infarction, acute coronary syndromes (including unstable angina, coronary artery bypass graft, coronary angioplasty or stenting) within 6 months prior to start of study treatment.*
 - b. Congestive heart failure requiring treatment (New York Heart Association \geq Grade 2).*
 - c. Persistent systolic blood pressure >150 mmHg or diastolic blood pressure >100 mmHg despite optimal antihypertensive therapy.*
 - d. History or presence of clinically significant cardiac arrhythmias (including uncontrolled atrial fibrillation or uncontrolled paroxysmal supraventricular tachycardia).*
 - e. History of congenital prolonged QT syndrome or mean triplicate baseline QT interval corrected for pulse rate using Fridericia's formula (QTcF interval) ≥ 480 ms.*
10. Participants with active Hepatitis B virus (HBV) or Hepatitis C virus (HCV) or any other severe viral active infection (e.g. severe acute respiratory syndrome coronavirus 2 [SARS-CoV-2] infection).
Active hepatitis is defined as:
 - Combination of HBV deoxyribonucleic acid (DNA) >1000 IU/mL or >2500 copies/mL plus positive Hepatitis B surface antigen (HBsAg) plus positive Hepatitis B core antibody.
 - Combination of HBV deoxyribonucleic acid (DNA) >1000 IU/mL or >2500 copies/mL plus positive Hepatitis B surface antigen (HBsAg)
 - Combination of HBV deoxyribonucleic acid (DNA) >1000 IU/mL or >2500 copies/mL plus positive Hepatitis B core antibody.
 - Positive serum HCV ribonucleic acid (RNA) and antibody to HCV (HCV Ab).
11. Evidence of active, non-infectious pneumonitis, history of interstitial lung disease that required oral or intravenous glucocorticoid steroids for management.

12. Known history of a positive test for human immunodeficiency virus (HIV) or known acquired immunodeficiency syndrome (AIDS). Testing for HIV must be performed at sites where mandated locally.
13. Participants who have had major surgery (e.g. inpatient procedure with regional or general anesthesia) within 6 weeks prior to start of study treatment.
14. Previous or concurrent malignancy within 2 years of study entry.

Except:

- a. *Bowen's disease.*
- b. *Cured basal cell or squamous cell skin cancer.*
- c. *Gleason 6 prostate cancer.*
- d. *Treated in-situ carcinoma of cervix.*

15. Participant's conditions that contraindicates the use of study treatment and may affect interpretation of results or that may render the participant at high risk from treatment complications.

Note:

Conditions are, in the opinion of the investigator, any medical or psychiatric conditions, metabolic dysfunction, physical examination finding or clinical laboratory finding suggesting disease/condition.

16. Pregnant (confirmed by positive serum β -HCG test), lactating or breast-feeding women.
17. Is a family member of the Investigator or any associate, colleague, and employee assisting in the conduct of the study (secretary, nurse, technician).
18. Is in a position likely to represent a conflict of interest.

